2 STUDY DESCRIPTION

2.1 Study Design

This study is a randomized, double-blind, placebo-controlled, parallel arm clinical trial in subjects receiving acetylsalicylic acid (ASA) with a recent Acute Ischemic Stroke (AIS) or Transient Ischemic Attack (TIA).

The study consists of two parts. Part 1 will have a treatment duration of 28 days. Part 2 will begin once results from ongoing toxicology studies are reviewed, and will have a treatment period of 90 days. Subjects enrolling in Part 1 will not be allowed in Part 2. The figures below illustrate the treatment plan for both study parts.

Figure 2.1-1: Study Design Schematic for Part 1

CV006-004 Study Schematic - Part 1 of study

[figure not shown]
[figure not shown]

Figure 2.1-2: Study Design Schematic for Part 2

CV006-004 Study Schematic - Part 2 of study

2.2 Treatment Assignment

At the screening visit each subject will be assigned a unique sequential subject number by the Interactive Voice Response System (IVRS). The subject number will consist of 5 digits which are assigned sequentially (00001, 00002, 00003, etc.) by the IVRS. This number will be used for

identification throughout the study and will not be used for any other participant. Screening of subjects with lacunar infarcts will be capped at approximately 20%.

In addition to the two Parts of the study noted above, which are related to treatment duration, the study also consists of two phases, each with a slightly different method of assigning study treatment. In Phase A, subjects will be randomized 1:1:1 using IVRS to one of two doses of BMS-986141 (0.8 mg or 4.8 mg) or placebo. In Phase B, subjects will be randomized 1:1:1:1 via IVRS to one of three doses of BMS-986141 (0.8 mg, 4.8 mg, or 8 mg) or placebo. The transition from Phase A to Phase B of the study will only occur after an Independent Data Monitoring Committee (DMC) has reviewed data from the first 10% of the planned subjects (approximately 132 subjects with 28 days of data). As of the time of the writing of this SAP, the decision to move from Part 1 to Part 2 of the study has been made. Some sites will continue to enroll subjects in to Part 1 of the study until Part 2 can be fully implemented. As a result, there will be no subjects randomized in Phase B during Part 1 of the study.

Randomization schedules will be generated by BMS and kept by the IVRS vendor. All subjects will receive open-label ASA at a dose from 75 to 162 mg per day beginning at a time consistent with local standards of care for patients with AIS or TIA. As mentioned in [section 2.1](#), the planned study dosing duration is 28 days for Part 1 of the study and 90 days for Part 2 of the study.

At all study visits when study drug is dispensed, each subject will be assigned a container number by the IVRS. Container numbers will be assigned non-sequentially and will correspond to the numbers printed on the packages and bottles containing study drug, and will be recorded on the appropriate eCRF. The IVRS will be available 24 hours per day, 7 days a week.

2.3 Blinding and Unblinding

2.3.1 Blinding

Blinding of treatment assignment is critical to the integrity of this clinical study. However, in the event of a medical emergency or pregnancy in an individual subject in which knowledge of the investigational product is critical to the subject's management, procedures are in place to have the blind broken for an individual subject.

Except as noted, BMS Research and Development personnel, as well as all vendors responsible for the conduct of the trial (protocol team) will remain blinded for the duration of the trial. The Data Monitoring Committee (DMC) will assess safety on an ongoing basis, and will have access to unblinded treatment codes. An analysis team, including a reporting statistician and programming support, who are not involved with the conduct of the study, will provide analyses to the DMC. This unblinded analysis team will not provide any information from unblinded analyses to the protocol team until after the trial has been completed.

The Bioanalytical Sciences section or its designate will be unblinded to the randomized treatment assignments in order to minimize unnecessary analysis of samples from control group subjects. Likewise, the Biotransformation section or its designate may be unblinded, if

metabolite profiling work is conducted. This unblinded analysis team will not provide any information from unblinded analyses to the protocol team until after the trial has been completed.

Platelet aggregation data will be collected and reviewed for QC purposes by hospital and vendor personnel not associated with the clinical conduct of the study. During the double-blind treatment period, platelet aggregation will be masked to the Investigator and protocol team. One biomarker representative, may be unmasked to review the platelet aggregation data, and will not provide any information that can potentially be unblinding to the protocol team until after the trial completes. The unmasked platelet aggregation data will be provided to the study team after the trial has been completed.

2.3.2 Unblinding

For this study, the method of unblinding for emergency purposes is IVRS. Details are included in the IVRS manual.

2.4 Protocol Amendments

A protocol revision was formally issued on 07-July-2016, incorporating several design changes into the study. Most notably, the original planned high dose of BMS-986141 was reduced from 16 mg to 8 mg, and this arm of the study is to be closed off until the Data Monitoring Committee is able to evaluate sufficient safety data from the 2 lower dose groups (0.8 mg and 4.8 mg). To that effect, the randomization scheme was updated to keep the 8mg arm closed until the DMC convened. Pending the outcome of the DMC meeting, the 8mg arm would open and randomization would proceed in a 1:1:1:1 fashion from there forward to one of the three BMS-986141 doses or placebo (see [Table 5-1](#)).

Additional updates were made to clarify various aspects of the study and can be found in the protocol revision. No further updates had a significant impact to the statistical methods planned for this study.

3 OBJECTIVES

3.1 Primary

The primary objective of the study is to determine the dose-response relationship of BMS-986141 on the recurrence of brain infarction at 28 days as assessed by a composite of symptomatic ischemic stroke and unrecognized brain infarction as assessed by MRI in subjects with ischemic stroke or TIA treated with ASA.

3.2 Secondary

- To assess the effect of BMS-986141 on the occurrence of major adverse cardiovascular events (MACE, including all stroke, myocardial infarction, and CV death) by Day 90
- To assess the effect of BMS-986141 on the occurrence of the composite of ischemic stroke, myocardial infarction, and CV death by Day 90
- To assess the effect of BMS-986141 on incidence of symptomatic recurrent ischemic stroke up to 28 days of treatment

- To assess the effect of BMS-986141 on the occurrence of the composite of unrecognized brain infarction assessed by MRI at Day 28 and MACE by Day 90

3.3 Safety

- To assess the effect of BMS-986141 on the composite of Major and Clinically Relevant Non-Major (CRNM) Bleeding
- To assess the effect of BMS-986141 on all reported bleeding
- To evaluate safety and tolerability of BMS-986141

3.4 Exploratory

- [REDACTED]

4 ENDPOINTS

4.1 Primary Efficacy Endpoint

The primary efficacy endpoint of the study is the incidence of a composite of symptomatic ischemic stroke by Day 28 and unrecognized brain infarction assessed by MRI at Day 28. Each of these will be assessed by an adjudication committee. If a subject experiences any of these events, the subject will be counted as having experienced a composite event in the analysis.

In the event that one, but not both of the components of the primary endpoint cannot be ascertained, then the remaining component will be evaluated. In this case, if the remaining component is counted as an event, the composite event will be considered as having occurred. If, however, the remaining component is not counted as an event, or if both of the components of the primary endpoint cannot be ascertained, the resulting primary endpoint will be considered as missing.

4.1.1 Symptomatic Stroke

All cases of suspected recurrent stroke will be adjudicated by a blinded Clinical Events Adjudication Committee (CEC). Diagnosis of stroke will require the abrupt onset of focal

neurological symptoms lasting at least 24 hours. Evaluation and treatment of strokes will be according to the local standard of care. It is strongly recommended (but not required) that an imaging procedure such as a CT scan or MRI be performed to evaluate events of suspected stroke or TIA.

Adjudicated strokes will be categorized by the CEC as definite ischemic, definite hemorrhagic, hemorrhagic transformation or type uncertain. Additional classification of stroke subtypes will be specified in the CEC charter.

4.1.2 Unrecognized Brain Infarction

MRI of the brain will be obtained in all subjects no later than within 24 hours of randomization and at the Day 28 visit. The baseline and Day 28 MRIs for each subject will be reviewed independently by the blinded neuroradiologists of the Imaging Adjudication Committee (IAC) to determine if any new areas of infarction have developed since the baseline MRI. These independent assessments will undergo adjudication according to the processes described in the Imaging Charter with a single, adjudicated determination recorded for each subject.

4.2 Secondary Efficacy Endpoints

Secondary endpoints include:

- The incidence of Major Adverse Cardiovascular Events (MACE) by Day 90, defined as a composite of adjudicated recurrent stroke, myocardial infarction, or cardiovascular-related death (CV death)
- The incidence of a composite of adjudicated recurrent ischemic stroke, myocardial infarction, or CV death by Day 90
- The incidence of adjudicated symptomatic recurrent stroke (including fatal and non-fatal) by Day 28
- The incidence of the composite of unrecognized brain infarction assessed by MRI at Day 28 and MACE by Day 90

Myocardial Infarction and cardiovascular death will be adjudicated by the Clinical Events Adjudication Committee (CEC). As the composite secondary endpoints are each defined in the list above, if a subject experiences any of these events, the subject will be counted as having experienced a composite event in the analysis.

4.3 Exploratory Endpoints

[REDACTED]

[REDACTED]

[REDACTED]

[REDACTED]

- [REDACTED]

4.4 Primary Safety Endpoint

The primary safety endpoint is incidence of a composite of adjudicated major bleeding and adjudicated Clinically Relevant Non-Major (CRNM) bleeding during the treatment period. If a subject experiences any of these events, the subject will be counted as having experienced a composite event.

4.5 Additional Safety Endpoints

Additional safety endpoints include the incidence of adjudicated major bleeding events, all bleeding events, intracranial hemorrhage events, as well as the incidence of AEs and markedly abnormal standard clinical laboratory test results. As well, vital signs, ECG results, physical exam findings, and certain renal parameters and biomarkers, including estimated glomerular filtration rate (eGFR), Cystatin-C, NGAL, and KIM-1 may be considered as additional safety endpoints.

5 SAMPLE SIZE AND POWER

The primary efficacy endpoint of the study is the incidence of a composite of symptomatic ischemic stroke by Day 28 and unrecognized brain infarction at Day 28. Sample size calculations were performed for detecting a dose-response effect with the MCP-MOD methodology using simulations with the DoseFinding package in R⁴. Simulations of 1000 clinical trials were performed, assuming a true incidence for placebo of 14%, a maximum relative risk reduction of 30% for BMS-986141 8 mg relative to placebo, and relative reductions of 75% and 90% of the maximum for the 0.8 and 4.8 mg doses, respectively. Candidate models included an Emax model and a logistic model.

Initially, randomization will be limited to the two lower doses of BMS-986141 (0.8 mg or 4.8 mg) or placebo in a 1:1:1 ratio until after the DMC review of safety and laboratory data from the Day 28 study visit for at least 10% of planned total subjects (approximately 132 subjects). If the DMC recommends proceeding to inclusion of the highest dose (8 mg), subsequent randomization will be in a 1:1:1:1 ratio. Based on the staggered randomization as shown in in the table below and the assumptions above, the study will have at least 80% power to demonstrate a dose-response relationship, using a 1-sided type I error rate of 15%. A total sample size of 1312 randomized subjects accounts for about 5% of subjects without post-randomization data.

Table 5-1: Randomization Targets

	Placebo	0.8 mg	4.8 mg	8 mg
Prior to interim safety review by the DMC: 132 subjects (1:1:1 randomization ratio)	44	44	44	0
Additional subjects randomized while interim safety reports are being generated and reviewed by the DMC (not included in the DMC safety interim analysis): 100	34	33	33	0

Table 5-1: Randomization Targets

	Placebo	0.8 mg	4.8 mg	8 mg
subjects (1:1:1 randomization ratio)				
After interim safety review by DMC: 1081 subjects	270	270	270	270
Total: 1312 subjects	348	347	347	270

Note: Numbers shown for each treatment group are estimates based on randomization ratio. Actual numbers could be slightly different based on randomization block size and rate of enrollment.

6 STUDY PERIODS, TREATMENT REGIMENS AND POPULATIONS FOR ANALYSES

6.1 Study Periods

As outlined in [section 2.1](#), the study will be conducted in two parts.

In Part 1 of the study, the treatment period will be 28 days. Part 2 of the study will only be initiated after regulatory review of reports from 90-day nonclinical toxicology studies that are currently ongoing. The treatment period in Part 2 will be 90 days. Subjects that are entered into Part 1 of the study will not be allowed to enter into Part 2.

Periods for each part of the study include pre-treatment, on-treatment, and post-treatment. Schematics for each study part are provided in Section 2.1.

6.2 Treatment Regimens

Study treatments will be assigned according to the details provided in [section 2.2](#) of this SAP.

6.3 Populations for Analyses

The analyses will use several populations as defined below.

- 1) All Enrolled Subjects: Includes all subjects who signed informed consent.
- 2) All Randomized Subjects / Intent to Treat (ITT) Population: Includes all subjects who were randomized to a treatment, regardless of whether they received study drug or not. This population will be analyzed according to the treatment assigned at randomization.
- 3) All Evaluable Subjects: Includes All Randomized Subjects as above, excluding those subjects' visits where relevant protocol deviations occurred, as defined in [Section 7.2.2](#).
- 4) All Treated Subjects: Includes all subjects who received at least one dose of study medication. This will be the primary population used in safety analyses and will be analyzed according to the treatment assigned at randomization, except in the following cases:
 - If a subject received the same incorrect treatment throughout the study (until either Day 28 or Day 90, or until discontinuation of the study drug), then the subject will be analyzed based on the treatment received.

- If a subject received study drug from more than one treatment group, and none of the administrations were consistent with the assigned randomized treatment group, then the subject will be analyzed based on the first treatment received.
- 5) Pharmacodynamics (PD) Population: A subset of the ITT Population that includes subjects with at least one pharmacodynamic endpoint assessed following the first dose of BMS-986141.
 - 6) Pharmacokinetic (PK) Population: Includes all subjects treated with BMS-986141 who also have at least one post-dose PK sample. The Evaluable PK Population is further defined as a subset of the PK Population including subjects who have adequate PK profiles on Day 1.

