3.3.1 Inclusion Criteria

1. Signed Written Informed Consent

- a) Subjects or Legally Acceptable Representatives (LAR), must be willing and able to give signed and dated written informed consent. (Note: Consent by a LAR will only be allowed if permitted by local regulations.)

2. Target Population

- a) Either acute ischemic stroke or high-risk TIA as defined here
 - i) Acute ischemic stroke, defined as:
 - (1) Neurological deficit attributed to the focal brain ischemia, and either of the following:
 - Persistent signs or symptoms of the ischemic event at the time of randomization
 - Acute, ischemic brain lesion documented by computed tomography (CT) scan or MRI

AND

(2) National Institutes of Health Stroke Score (NIHSS) ≤ 7

ii) High-risk TIA, defined as:

(1) Neurological deficit of acute onset attributed to focal ischemia of the brain by history or examination with complete resolution of the deficit, and at least one of the following:

- ABCD2 score ≥ 4 OR motor or speech symptoms
- Symptomatic intracranial arterial occlusive disease documented by transcranial Doppler, ultrasound or vascular imaging, defined as at least 50% narrowing in diameter of a vessel that could account for the clinical presentation
- Documented internal carotid arterial occlusive disease, defined as at least 50% narrowing in diameter of a vessel that is presumed to be atherosclerotic and could account for the clinical presentation
- Documented stenosis in the vertebral circulation that is presumed to be atherosclerotic and could account for the clinical presentation

- b) CT or MRI ruling out hemorrhage or other pathology, such as vascular malformation, tumor, or abscess that could explain symptoms or contraindicate therapy
- c) Randomization occurring within 48 hours after onset of symptoms; if the time of onset of symptoms is unknown, such as when symptoms are first present on awakening, onset should be considered as time last seen normal
- d) Subject is able to be evaluated by study-specific MRI no later than 24 hours after randomization, does not have contraindications to the performance of the MRI, and has suitable weight and circumference. See [Section 3.4.3](#) for further details.
- e) Ability to tolerate ASA at a dose from 75 to 162 mg/day
- f) Subject Re-enrollment: This study does not permit the re-enrollment of a subject that has discontinued the study as a pre-treatment failure

3. Age and Reproductive Status

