- d) Planned use of antiplatelet therapy other than study medication or ASA at a dose from 75 to 162 mg. including ASA at a dose < 75 mg/day or > 162mg/day, GPIIb/IIIa inhibitors, clopidogrel, ticlopidine, prasugrel, dipyridamole, ozagrel, cilostazol, and ticagrelor. Treatment with ASA at a dose >162 mg/day before randomization is allowed.
- e) Receipt of any intravenous or intra-arterial thrombolysis within 48 hours of randomization (This criterion is Not Applicable per Protocol Amendment 06; refer to Exclusion Criteria 2o)
- f) Anticipated requirement for ongoing treatment with non-steroidal anti-inflammatory drugs (NSAIDs). COX-2 inhibitors are allowed. NSAID use prior to randomization is allowed
- g) Use of strong CYP3A4 inhibitors or strong CYP3A4 inducers in the 7 days prior to randomization or the need for ongoing treatment with concomitant oral or intravenous therapy with strong CYP3A4 inhibitors or strong CYP3A4 inducers during the study.

Eligibility criteria for this study have been carefully considered to ensure the safety of the study subjects and that the results of the study can be used. It is imperative that subjects fully meet all eligibility criteria.

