7.2.2 Relevant Protocol Deviations

Relevant deviations from the study protocol will be documented and accounted for in presenting the data summaries, listings and descriptive statistical analyses. Any changes from planned protocol-specified analyses will be defined in the SAP and reported in the CSR. The relevant protocol deviations are described in the table below.

Table 7.2.2-1: List of Relevant Protocol Deviations

Number	RPD Criteria
1	Subject randomized but not dosed
2	Error in treatment assignment (resulting in a subject receiving a treatment other than that assigned by the IVRS) during the first 28-day interval
3	Poor treatment compliance for either BMS-986141 or ASA (compliance less than 80% or more than 120%) during first 28-day interval
4	Randomized subjects with history of atrial fibrillation (AF) other than transient AF related to cardiac surgery at enrollment (per Exclusion Criteria 1a from the protocol)
5	Randomized subjects with unrecognized or misdiagnosed intracranial hemorrhage (ICH) as determined by the central reader based on the baseline study specific MRI (presence of type 1 or 2 parenchymal hematoma)
6	Randomized subjects who took no dose of ASA or dose of ASA not within limits designated by the protocol for ≥ 5 consecutive days in the first 28 days of the treatment period
7	Randomized subjects who took oral anticoagulants or prohibited antiplatelet therapy, other than study medication, for > 2 consecutive days during the first 28days of the treatment period
8	Randomized subjects that were treated with a strong CYP3A4 inhibitor for > 5 days during the first 28 days of the treatment period ^a

a: CYP3A4 inhibitors will be defined in a separate file maintained by the study team and will be classified as weak, moderate, or strong.

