7.5.1.1 Sensitivity Analyses

To assess the robustness of the primary efficacy analysis, additional sensitivity analyses will be carried out using the following approaches:

- Following the same procedure as the primary analysis, considering the All Evaluable Subjects population in place of the All Randomized Subjects population.
- A worst-case analysis that will repeat the primary analysis on the ITT population where any missing information that is consequential to the evaluation of the primary endpoint will be considered as an event.

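### The evaluable set for the Day 28 sensitivity analysis removes visits, a rule that does not work for a once-per-subject endpoint, and its deviation list leaves out strong CYP3A4 inducers

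*SAP*

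**What the plan says.** SAP 6.3 item 3 takes all randomized subjects, "excluding those subjects' visits where relevant protocol deviations occurred". SAP 7.5.1.1 uses this set for the first of two sensitivity analyses of the primary endpoint, "considering the All Evaluable Subjects population in place of the All Randomized Subjects population". The second counts consequential missing information as an event.

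SAP 4.1 scores the primary composite once per subject. If one component cannot be ascertained, the other decides: an event there makes the composite an event; otherwise the composite is missing.

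The deviations are the eight items of SAP Table 7.2.2-1. Two concern eligibility: item 4, "Randomized subjects with history of atrial fibrillation (AF) other than transient AF related to cardiac surgery at enrollment", and item 5, parenchymal hematoma on the baseline study MRI. The other six concern dosing, treatment assignment, compliance, ASA, prohibited antithrombotics and CYP3A4 inhibitors. Item 8 reads "Randomized subjects that were treated with a strong CYP3A4 inhibitor for > 5 days during the first 28 days of the treatment period".

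Protocol exclusion 6g names both drug classes: "Use of strong CYP3A4 inhibitors or strong CYP3A4 inducers in the 7 days prior to randomization". Protocol 3.4.1 and 3.5 also treat strong inhibitors and strong inducers together.

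**The concern.** A visit-level exclusion suits an endpoint measured repeatedly. Here there is one outcome per subject, and the SAP does not say which visit a deviation removes or how the composite is then derived. Two programmers could follow the text and obtain different data sets. The two most direct readings either keep subjects the set seems meant to drop, or keep deviators only when they had a stroke.

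The inducer gap matters because the trial is about dose-response. Protocol 1.4.1 reports that a strong CYP3A4 inhibitor raised exposure up to 8-fold. An inducer would be expected to act in the opposite direction, although the documents give no figure for it. The list captures only one of the two classes.

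At stake is how a comparison is read. Within the SAP this is the only sensitivity analysis based on deviations, so agreement with the ITT result could be taken as robustness that was not tested, and disagreement could come from the way the set was built.

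**Working it through.** **Planned figures.** None depends on this set. The 1240 evaluable subjects in the protocol synopsis are those with post-randomization data, a different use of the word: 1240/1312 = 94.5%, so the allowance is 5.5%, in line with the stated loss of about 5% (1240/0.95 gives 1306).

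**Step 1: can a deviation be placed at a visit?** Items 1, 4 and 5 are subject statuses (not dosed, AF history, hemorrhage at baseline). Items 2, 3, 6, 7 and 8 are conditions over the first 28 days. None is tied to a visit.

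**Step 2: apply the literal rule.**

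| Reading | AF history (item 4) | Baseline hemorrhage (item 5) | 28-day conditions (items 2, 3, 6, 7, 8) |
|---|---|---|---|
| Remove the visit where the deviation arose | Enrollment visit goes; Day 28 composite stays | Subject stays, or loss of the baseline MRI makes the MRI component unascertainable | No single visit to remove |
| Remove the Day 28 visit | MRI component lost; SAP 4.1 applies | Same | Same |

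Under the second reading an adjudicated symptomatic ischemic stroke still counts, because it is an event record and not a visit measurement. Every other deviator becomes missing. Deviators can then enter the analysis only as events.

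**Step 3: size of the second reading.** The true rate is p = 0.14 (placebo assumption, SAP 5). The documents do not give the share of deviators d or the share of events that are symptomatic s, so both are assumed: d = 5% to 20%, s = 20% to 50%.

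Apparent rate = [(1 − d)p + d·p·s] / [(1 − d) + d·p·s]

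- Low end, d = 0.05, s = 0.2: (0.1330 + 0.0014)/(0.9500 + 0.0014) = 14.1%.
- High end, d = 0.20, s = 0.5: (0.112 + 0.014)/(0.800 + 0.014) = 15.5%.

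| d | s = 20% | s = 30% | s = 50% |
|---|---|---|---|
| 5% | 14.1% | 14.2% | 14.3% |
| 10% | 14.3% | 14.4% | 14.7% |
| 20% | 14.6% | 14.9% | 15.5% |

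If deviations were unequal, say 5% on placebo and 15% on active (again assumed), the same formula by arm gives a relative risk of 1.02 to 1.05 when the truth is 1.00, and 0.716 to 0.739 when the truth is 0.70. Reversing the imbalance reverses the direction.

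**Step 4: inducers.** Exclusion 6g, the discontinuation rule in 3.4.1 and the discontinuation list in 3.5 each name strong inducers beside strong inhibitors. Table 7.2.2-1 item 8 and its footnote on the classification file name inhibitors only.

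**Step 5: entry criteria not on the list.** Of eight disease-defining items (inclusion 2a to 2c, exclusion 1a to 1e), five have no listed deviation: 2a, 2c, 1b, 1c and 1d. If 2% to 8% of 1312 subjects (26 to 105) breached one and had no drug effect at the same event rate, the 30% relative reduction would appear as 30% × 0.98 = 29.4% to 30% × 0.92 = 27.6%. For scale, planned arms of 348 and 270 with rates of 14% and 9.8% give SE(log RR) = √(0.86/48.72 + 0.902/26.46) = 0.23, so a 95% interval for the 8 mg reduction of about −9% to 55%.

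**The case against.** The set is named for subjects, and items 4 and 5 are worded at subject level. AF history does not end at screening, so one may fairly read the rule as removing every visit of such a subject. A reader might infer from the literal text that the eligibility deviations remove nobody; that is one reading among several, and the documents do not settle it. What stands is that the text does not select a workable reading.

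A reader might also infer that this is an eligibility-based analysis that fails because most entry criteria are missing from the list. The SAP does not say so. Its stated purpose is general, "To assess the robustness of the primary efficacy analysis, additional sensitivity analyses will be carried out", and six of the eight items concern trial conduct. Restricting relevant deviations to a selected subset is a choice that no other passage contradicts. The set may contain ineligible subjects, but the documents give no counts, and step 5 shows a small effect even with the extreme assumption of no drug effect in every breaching subject.

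Nor is this the only sensitivity analysis planned across both documents. Protocol 8.4.2.1 has one restricted to treated subjects with an evaluable Day 28 MRI or an adjudicated stroke. It concerns treatment and data availability, does not address most listed deviations, and is not carried into SAP 7.5.1.1.

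Finally, excluding subjects for any deviation at any time has its own bias. Prohibited antiplatelet or anticoagulant use (item 7) may begin because of a recurrent stroke, and the item makes no exception for use after an event. That objection is sound, and the fix must meet it.

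**Conclusion.** The concern holds in a limited form. The visit-level definition misfires for the Day 28 composite: under direct readings of the text, listed deviators either stay in or contribute events only. The second outcome inflates a 14.0% rate to about 14.1% to 15.5%, and shifts the relative risk by a few hundredths if deviations are unbalanced as assumed. These sizes rest on assumed deviation shares and symptomatic shares. The omission of strong inducers from item 8 is a plain mismatch with the protocol; its size cannot be estimated from the documents.

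The fuller list of entry criteria is a matter of preference. Everything here is confined to one sensitivity analysis. The primary test is ITT (SAP 7.5), and its one-sided alpha of 0.15 and planned 1312 subjects do not change. The correction is worth making because it is cheap and removes a result that could be misread.

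**What to change.** Before unblinding, amend the SAP as follows.

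1. In 6.3 item 3, define the set at subject level for the Day 28 composite: a subject with a relevant deviation leaves both numerator and denominator.
2. Count post-randomization deviations (items 3, 6, 7 and 8) only if they occur before any adjudicated primary-endpoint event, so that nobody is removed because of the outcome. For an unrecognized infarct, which has no onset date, the Day 28 scan date can serve; compliance in item 3 would be computed up to the event.
3. Extend Table 7.2.2-1 item 8 to strong CYP3A4 inducers.

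Optional: add a baseline study MRI taken more than 24 hours after randomization, since that scan is the reference for new infarction (the timing also appears in inclusion 2d, "Subject is able to be evaluated by study-specific MRI no later than 24 hours after randomization"), and the main disease-defining breaches: the 48-hour window, NIHSS, qualifying TIA and exclusion 1b. If these are left out, a sentence giving the reason is enough.

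The cost is SAP wording, some programming and a list of inducers beside the existing inhibitor file; concomitant medications are already coded (SAP 7.4.4). The downside is a smaller sensitivity set.
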